## **9.3** INTERIM ANALYSES

No interim analysis will be performed. Data for all subjects from Groups 1 and 2 who either completed or discontinued prematurely from this open label study will be cleaned and locked. The data will then be analyzed according to the SAP and the results may be presented in a preliminary report. Regardless of the analysis results, no additional subjects will be enrolled into Groups 1 and 2.

Data from subjects in Group 3 will continue to be cumulated after data from subjects in Groups 1 and 2 are locked. After all subjects in Group 3 are either completed or discontinued prematurely from this open label study, these data will be cleaned and locked. The final analyses from all data from Groups 1, 2, and 3 will be performed according to the SAP after Group 3 data are locked. The formal results of the study will be presented in the CSR.

## **9.4** ADJUSTMENTS FOR MULTIPLICITY

As the efficacy evaluation is for exploratory purpose only, no adjustment for multiple testings will be made.

## 9.5 POWER AND SAMPLE SIZE JUSTIFICATION

At least 20 subjects, but no more than 24 subjects, will be enrolled to Group 1 (CAM2038 q1w). Approximately 16 subjects will be enrolled to each of Group 2 (128 mg CAM2038 q4w) and Group 3 (160 mg CAM2038 q4w), for a total of approximately 32 subjects administered CAM2038 q4w.. These sample sizes are consistent with typical PK studies. Replacement subjects may be added at the discretion of the Sponsor with the agreement of the Principal Investigator.

## **10.0** SUMMARIES OF PHARMACOKINETIC ANALYSIS

## **10.1** PHARMACOKINETIC PARAMETERS

PK parameters of BPN and its active metabolite norBPN will be estimated using Phoenix® WinNonlin® (Certara, L.P., [name]), version 6.4 or higher. Standard noncompartmental methods and actual dates and times of dosing and blood sampling will be used in the calculations. The following PK parameters will be determined for BPN and norBPN (if applicable):

Group 1:

- AUCss (area under the plasma concentration-time curve during a 7-day dosing interval at steady state) for each injection site, i.e., buttock (reference), abdomen, thigh and back of upper arm
- $\circ$  Average plasma concentration during a dosing interval at steady state (Css,av) for each injection site, i.e., buttock (reference), abdomen, thigh and back of upper arm
- Maximum observed plasma concentration during a dosing interval at steady state ( $C_{ss,max}$ ) for each injection site, i.e., buttock (reference), abdomen, thigh and back of upper arm
- Time to Css,max (tss,max) for each injection site, i.e., buttock (reference), abdomen, thigh and back of upper arm.
- $\circ$  Trough concentration Css,trough measured prior to the next actual dose or next scheduled hypothetical dose at steady state.
- norBPN/BPN ratios for AUCss and Css,max for each injection site, i.e., buttock (reference), abdomen, thigh and back of upper arm.

#### Group 2:

- AUCss (AUC during a 28-day dosing interval at steady state)
- o Css,av
- o Css,max
- o tss,max
- o Css,trough
- %Fluctuation
- $\circ$  norBPN/BPN ratios for AUCss and Css,max

#### Group 3:

- AUCss (AUC during a 24-hour (SL BPN) and 28-day (CAM2038 q4w) dosing interval at steady state)
- o Css,av
- $\circ$   $C_{ss,max}$
- $\circ$   $t_{ss,max}$
- $\circ \quad C_{ss,trough}$
- %Fluctuation
- $\circ$  norBPN/BPN ratios for AUC\_{ss} and C\_{ss,max}

 $AUC_{ss}$  will be calculated using the linear trapezoidal method up to  $C_{ss, max}$  and the logarithmic trapezoidal method for the remainder of the curve up to 168 hours after dose for CAM2038 q1w, 672 hours after dose for CAM2038 q4w and 24 hours after dose for SL BPN.

 $C_{ss,av}$  will be calculated as AUCss/ $\tau$ , where  $\tau$  is the dosing interval (168 hours for CAM2038 q1w, 672 hours for CAM2038 q4w and 24 hours for SL BPN.

%Fluctuation will be calculated as  $(C_{ss,max} - C_{ss,min})*100/C_{ss,av}$  for CAM2038 q4w and SL BPN, where  $C_{ss,min}$  is the minimum plasma concentration during a dosage interval at steady state (4th dose for CAM2038 q4w and 7th dose for SL BPN).

The norBPN/BPN ratios for AUCss and  $C_{ss,max}$  will be adjusted for differences in molecular weight between buprenorphine (molecular weight 467.64 g/mol) and norbuprenorphine (molecular weight 413.55 g/mol).

Plasma concentration levels of BPN and norBPN assessed prior to next actual or hypothetical dose  $(C_{trough})$  will be assessed after Dose 1 to 7 in Group 1 and after Dose 1 to 4 for CAM2038 q4w in Groups 2 and 3.

Unless otherwise stated, PK data will be analyzed by a third party Clinical Research Organization (CRO), Worldwide Clinical Trials. PK results will be produced by the CRO in a separated report. The PK results will also be discussed in the Clinical Study Report (CSR) by reference to the PK report.

## **10.2** HANDLING OF VALUES BELOW THE LLOQ

Plasma concentration values below the limit of quantification (LLOQ) will be assigned a value of zero when they preceedprecede the first quantifiable sample. Values below LLOQ embedded between two quantifiable data points or occuring after the last quantifiable concentration will be treated as missing data.

## **10.3** ANALYSIS OF PHARMACOKINETICS

Summaries of plasma concentrations of BPN and norBPN will be presented for the PKEVAL population and PK population by group and injection site, if applicable. The following descriptive statistics will be presented at each nominal time point: n, arithmetic mean, standard deviation, and coefficient of variation percentage (CV%), median, geometric mean, geometric CV%, minimum and maximum values. Mean plasma concentration-time data will be displayed for the PKEVAL population and the PK population in linear and semi-logarithmic scales by group and injection site, if applicable. Individual plasma concentrations of BPN and norBPN will be listed for the PK population by group.

The PK parameters (Section 10.1) will be listed for the PK population and summarized for the PKEVAL population and PK population by group and injection site, if applicable. Summary statistics will include n, arithmetic mean, standard deviation, CV%, median, geometric mean, geometric CV%, minimum and maximum values.

For Group 1 (CAM2038 50 mg/mL q1w), the following considerations will apply in the PK analyses. The primary PK parameters will be  $AUC_{ss}$  and  $C_{ss,max}$  after steady state injections of CAM2038 q1w at different injection sites. The injection site buttock will be the reference. The analyses will be based on log-transformed data. The natural log-transformed AUCss and Css,max data will be analyzed using an ANOVA model, sequence, subject within sequence (1, 2, 3, 4 corresponding to A/B/D/C, B/C/A/D, C/D/B/A, D/A/C/B, where A=buttock, B=abdomen C=thigh, or D=back of upper arm), period, and

treatment sites (treatment sites: A=buttock, B=abdomen C=thigh, or D=back of upper arm). The estimated injection site effects, injection site differences versus the reference (B-A, C-A, and D-A), and the 90% confidence intervals of the estimated differences will be presented. The above estimates will be expressed on the raw scale (expressed after performing the anti-log).

No interim analysis will be performed. However, after all Groups 1 and 2 subjects either completed the study or discontinued from the study prematurely, the above analysis may be performed before subjects from Group 3 complete the study or discontinued from the study prematurely. Before the analysis is conducted all data records related to the PK parameters will be locked. Any changes to the records after the analysis will be discussed in the CSR. No additional subjects will be permitted to enter Groups 1 or 2 after the analysis is conducted.

For Groups 2 and 3 (CAM2038 q4w), the PK parameters will be summarized by descriptive statistics. The primary PK parameters will be AUCss and  $C_{ss,max}$ . Relative bioavailability of BPN will be assessed at steady state for 160 mg CAM2038 q4w vs 24 mg SL BPN by ANOVA with 90% confidence intervals tabulated for treatment differences (back transformed and expressed as a percentage).

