#### Methodology:

This is a Phase II, open-label, partially randomized, 3-treatment group, multi-site study designed to evaluate the steady state PK of BPN and norBPN following repeated SC administration of CAM2038 q1w (Group 1) at different injection sites, to evaluate the steady state PK of BPN and norBPN after repeated SC administration of CAM2038 q4w (Group 2 and Group 3), and to evaluate relative bioavailability of BPN following SC administration of 160 mg CAM2038 q4w as compared with 24 mg SL BPN (Group 3) in opioid-dependent

Clinical Study ProtocolBraeburn PharmaceuticalsHS-15-549CONFIDENTIALsubjects with a history of chronic non-cancer pain. The study will involve 4 phases: Screening, Treatment, openlabel safety extension and Follow-up.

Within 21 days of a medical Screening visit and confirmation of eligibility, subjects will be randomized to 1 of 2 treatment groups (Group 1 or Group 2; refer to Section 10.2, Eligibility Review and Randomization, for more detail):

- Group 1: 3 single weekly SC injections of 32 mg CAM2038 q1w (50 mg/mL) administered in the buttock to reach steady state, rotating between right and left buttock and injection site, followed by 4 single weekly SC injections of 32 mg CAM2038 q1w administered in the buttock (reference), abdomen, thigh, and back of upper arm in a randomized, crossover manner, with injection site sequence allocated using a randomized crossover design.
- Group 2: 4 monthly SC injections of 128 mg CAM2038 q4w (356 mg/mL) administered in the buttock, rotating between right and left buttock and injection site.

An additional group, to which subjects will not be randomized, was added following completion of randomization to Groups 1 and 2, in order to evaluate a higher dose of CAM2038 q4w (i.e., 160 mg) and compare resultant BPN exposure with SL BPN treatment:

 Group 3: 7 consecutive single daily doses of 24 mg SL BPN, followed by 4 monthly SC injections of 160 mg CAM2038 q4w (356 mg/mL) administered in the buttock, rotating between right and left buttock.

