## 5.1.2 CAM2038 q4w (Once Monthly)

The PK and safety of CAM2038 q4w has been investigated after single administration in a bridging clinical PK study in healthy volunteers versus repeat dose CAM2038 q1w (i.e. at steady state), repeat dose SL BPN (i.e. at steady state), and single dose of IV BPN (Study HS-13-487). The following conclusions can be drawn regarding the clinical properties of CAM2038 q4w:

- Extended BPN release over 4 weeks at target plasma concentrations
- Dose proportionality was shown within the dosage interval 64 to 192 mg CAM2038 q4w
- 6- to 8-fold higher bioavailability than SL BPN, comparable to CAM2038 q1w
- Observed BPN plasma concentrations over 4 weeks comparable to CAM2038 q1w over 1 week, and to SL BPN over 24 hours at steady state (i.e., for approved 8 mg, 16 mg, or 24 mg doses)
- Predicted Css,av and Css,trough values for 64, 96 and 128 mg CAM2038 q4w similar to CAM2038 q1w and SL BPN (i.e., for approved 8 mg, 16 mg, or 24 mg doses); and predicted exposure for 160 mg CAM2038 q4w similar to SL BPN 26 mg to 32 mg
- Safety profile comparable to reference IV and SL BPN treatments
- Good local tolerability

The most commonly reported drug-related AEs after CAM2038 q1w and CAM2038 q4w administration were nausea, dizziness and vomiting. The local tolerability was good with 6 subjects experiencing 7 AEs that were assessed as related to CAM2038 q4w (injections site reactions, injection site pain, injection site induration and application site bruise). Two SAEs were reported by 2 subjects after treatment with 192 mg CAM2038 q4w. The first SAE was an event of withdrawal reaction and the second SAE was an event of dehydration due to nausea and vomiting. Both SAEs were assessed as related to CAM2038 q4w (withdrawal reaction was also assessed as related to the concomitant treatment with naltrexone) and the event of withdrawal reaction qualified for reporting as a suspected unexpected serious adverse reaction (SUSAR). There were no deaths or any other significant AEs and most of the AEs were mild and transient. Analysis of clinical chemistry, hematology and urinalysis parameters did not suggest any significant safety issues for CAM2038 q4w.

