### Clinical Study Protocol HS-15-549

may be transferred to 32 mg of CAM2038 q1w and continue in an open-label extension phase for up to 6 weeks.

Group 3: 7 consecutive single daily doses of 24 mg SL BPN, followed by 4 monthly SC injections of 160 mg CAM2038 q4w (356 mg/mL) administered in the buttock, rotating between right and left buttock per Appendix 17.2. Note: 160 mg CAM2038 q4w (356 mg/mL) is estimated to be equivalent to 26 mg to 32 mg SL BPN.

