# 3.0 INTRODUCTION

This statistical analysis plan (SAP) is based on Protocol HS-15-549, Amendment 4: 5.0, 05 OCT 2016.

The purpose of this document is to provide details and clarifications on study populations and on how the variables will be derived, how missing data will be handled, as well as details on statistical methodologies to be used to analyze the pharmacokinetics (PK), safety and efficacy data from the study.

The document may evolve over time, for example, to reflect the requirements of protocol amendments or regulatory requests. However, the final SAP must be finalized, approved by the Sponsor, and placed on file before database is locked. Deviations from the final approved plan will be noted in the clinical study report.

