#### **5.3** EVALUABLE PHARMACOKINETIC POPULATION

Evaluable pharmacokinetic (PKEVAL) population will consist of all subjects in the PK population who have provided sufficient PK data for all 4 randomized injection sites to derive PK parameters of interested (Group 1), or have provided PK data after the last injections of CAM2038 q4w (Groups 2 and 3). All primary PK summaries will be based on the PKEVAL population.

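### Does the missing formula for Group 3 relative bioavailability in SAP 10.3, beside two protocol figures that do not quite meet, call for a change?

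*SAP*

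**What the plan says.** Relative bioavailability of BPN at steady state, 160 mg q4w against 24 mg SL, is a secondary objective (Protocol 6.2, SAP 4.1). Protocol 10.3.2 leaves the PK details to the SAP, and SAP 3.0 promises details "on how the variables will be derived, how missing data will be handled, as well as details on statistical methodologies to be used".

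SAP 10.3 names AUCss and Css,max as the primary parameters for Groups 2 and 3, then covers this comparison in one sentence: it will be assessed "by ANOVA with 90% confidence intervals tabulated for treatment differences (back transformed and expressed as a percentage". SAP 10.1 takes AUCss over 24 hours for SL BPN and 672 hours for q4w, and defines Css,av as AUCss divided by the dosing interval. SAP 5.3 admits a Group 3 subject to the evaluable set if they "or have provided PK data after the last injections of CAM2038 q4w (Groups 2 and 3".

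Protocol 5.1.2 reports "6- to 8-fold higher bioavailability than SL BPN, comparable to CAM2038 q1w". Two bullets later it gives "predicted exposure for 160 mg CAM2038 q4w similar to SL BPN 26 mg to 32 mg", and Protocol 7.1 repeats that "160 mg CAM2038 q4w (356 mg/mL) is estimated to be equivalent to 26 mg to 32 mg SL BPN". The same bullet in 5.1.2 also describes 64, 96 and "128 mg CAM2038 q4w similar to CAM2038 q1w and SL BPN (i.e., for approved 8 mg, 16 mg, or 24 mg doses". The Synopsis (Methodology) says Group 3 was added to study a higher q4w dose and "compare resultant BPN exposure with SL BPN treatment".

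**The concern.** There are two worries.

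First, the protocol appears to disagree with itself on the very quantity Group 3 estimates: the fold figure and the milligram equivalence give ranges that do not overlap.

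Second, the SAP sentence does not name the response variable, the normalisation or the model terms, although the two treatments differ in both dose (160 against 24 mg) and AUC interval (672 against 24 hours). A ratio of average exposures and a dose-corrected bioavailability are different numbers, and either could appear in a table as a percentage. The evaluable set does not require a Day 7 SL profile, so a within-subject comparison is not spelled out either.

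If the scale were open and could swing the reading, a secondary objective could be reported as confirming whichever background figure suited. Group 3 has the only planned SL profile in the study, so nothing else in the trial would correct that.

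**Working it through.** **Inputs.** q4w dose 160 mg on Days 8, 36, 64 and 92, so a 28-day interval (Protocol 7.1; 672 hours in SAP 10.1). SL dose 24 mg daily. Stated figures: 6- to 8-fold, and SL 26-32 mg (Protocol 5.1.2).

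**The two protocol figures.** The daily q4w dose is 160/28 = 5.714 mg. If 160 mg gives the same average exposure as SL d mg per day, dose-corrected relative bioavailability is F = 28d/160 = 0.175d.
- d = 26: F = 4.55. d = 32: F = 5.60.
- In reverse, 6/0.175 = 34.3 mg and 8/0.175 = 45.7 mg.

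The ranges do not overlap. The nearest ends differ by 6/5.60 = 1.07. The reverse conversion also needs SL exposure to be proportional to dose, which the documents do not state.

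**Does the choice of scale change the reading?** Let R be the Css,av ratio of q4w to SL 24 mg. Unadjusted AUCss gives 28R. Dose-corrected AUCss gives F = R x 28 x 24/160 = 4.2R. Take R = 1.20 as an example result.

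| | Css,av | Dose-corrected AUCss | Unadjusted AUCss |
|---|---|---|---|
| SL 26-32 mg | 108-133% | 455-560% | 3033-3733% |
| 6- to 8-fold | 143-190% | 600-800% | 4000-5333% |
| Example | 120% | 504% | 3360% |

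In every column the example lies inside the first range and below the second. The columns differ only by constants, so the same holds for any result. On the log scale a constant shifts the estimate and leaves the width of the interval unchanged.

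**Could the trial separate the nearest ends?** The documents give no variability, so assume n = 16, total CV 40-60% and within-subject correlation 0.3-0.7. With sigma = sqrt(ln(1 + CV²)) and a subject term, the 90% log-scale half-width is 1.753 x sigma x sqrt(2(1 - rho)/16). The interval is then the estimate times or divided by a factor of 1.14 to 1.33. Even the smallest factor exceeds 1.07. An estimate of 5.8 with factor 1.14 gives 5.09 to 6.61, which is compatible with both figures.

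**How firm is the gap?** Protocol 5.1.2 gives no SL reference dose for the 6- to 8-fold figure. If it was obtained against SL d mg and SL exposure rises as dose to the power b, the ranges meet at 32 mg when 0.175 x d x (32/d)^b = 6. That gives b = 1.05 for d = 8, 1.10 for d = 16 and 1.24 for d = 24. A modest departure from proportionality is enough if the reference was a low SL dose.

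**What the SAP sentence already fixes.** Back-transformation implies a log scale. AUCss is named as a primary parameter in the sentence before. Relative bioavailability ordinarily means AUC per unit dose. The Group 1 model in the same section carries a subject term. If subject is a fixed effect, anyone lacking one of the two profiles contributes nothing to the treatment contrast, so the looser evaluable set does no harm. A subject with data after the fourth injection has in any case already passed the scheduled Day 7 profile.

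**The case for a change.** The strongest case for a change is that the SAP undertakes to give derivations and here does not. Group 1 is specified in full, but its model cannot simply be carried over: Group 3 has one fixed order, so there is no sequence factor and period cannot be separated from treatment. Leaving out the subject term would matter. Under the same assumptions the interval factor without it is 1.26 to 1.40, and the log-scale width is 1.16 to 1.77 times that of the paired analysis. The centres of the two protocol ranges, sqrt(4.55 x 5.60) = 5.05 and sqrt(6 x 8) = 6.93, differ by a factor of 1.37, which is more than the 7% at the nearest ends. If the lower doses are paired in order with SL 8, 16 and 24 mg, they imply 3.50-, 4.67- and 5.25-fold, all below 6. Less-than-proportional SL exposure would widen the gap, as would reading the fold figure literally as 7 to 9. A few sentences would cost almost nothing.

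Part of this stands. The formula is absent, and the two ranges do not meet as written. But the width penalty is measured against an unpaired analysis that no document proposes, for data in which each subject receives both products. The in-order pairing is a reading the protocol does not state. With q4w exposure proportional to dose, 128 mg gives twice the exposure of 64 mg while SL 24 mg is three times SL 8 mg. So either those matches are loose or SL exposure is not proportional. The 26-32 mg statement is a prediction expressed as similarity, and the 6- to 8-fold figure is a conclusion from a study with single q4w doses. Neither is an input to any analysis.

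**Conclusion.** No change is needed. The SAP part is missing detail that a competent PK analyst supplies in the ordinary way: the log ratio of AUCss per mg within subject, with Css,av and Css,max ratios reported as exposure comparisons. If another scale were tabulated, a reader could convert it from the stated doses and intervals, and it would stand in the same relation to both protocol figures.

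The protocol part is a small mismatch between two approximate background statements: 4.55- to 5.60-fold against 6- to 8-fold, 7% apart at the nearest ends. This rests on a 28-day interval and on reading similar exposure as equal average concentration. The two statements should be reconciled, with the scale and SL reference dose of each given, whenever the background text is next revised. This note takes no view on which is right. That is editorial: no sample size, analysis set, acceptance limit or conclusion depends on it. The statement about precision rests on the assumed n, CV and correlation. The finding that the choice of scale cannot alter the reading needs no such assumption.

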# **11.0** SUMMARIES OF MEASURES OF SAFETY

Safety analyses will be performed for the safety population. Safety evaluations will be based on the incidence, intensity, and type of adverse events, as well as on clinically significant changes in the subject's physical examination, vital signs, and clinical laboratory results, Injection site examination and wound care. Safety variables will be tabulated and presented by study drug actually received.

Because there is no pre-specified safety outcome defined in terms of AEs, clinically relevant laboratory parameters, or vital signs, any formal comparisons between the treatment arms with respect to specific safety parameters will be post-hoc.

## **11.1** EXTENT OF EXPOSURE

Summary statistics (number and percentage) of weeks of exposure to study drug (i.e. from date of initial injection to the end of the study) will be tabulated by treatment group.,

## **11.2** COLUMBIA-SUICIDE SEVERITY RATING SCALE (C-SSRS)

Columbia-Suicide Severity Rating Scale (C-SSRS) will be summarized for the Safety Population.

## **11.3** COWS AND SOWS

Clinical Opioid Withdrawal (COWS) Scale, and Subjective Opioid Withdrawal (SOWS) Scale will be summarized over time by treatment group.

## **11.4** ADVERSE EVENTS

Each AE and SAE term recorded on the case report forms (CRFs) by primary system organ class (SOC) and will be mapped to a preferred term using the MedDRA dictionary. The investigator will assess AE severity and relationship to the study treatment.

A treatment emergent adverse event (TEAE) is defined as any AE with an onset date on or after date of randomization (Groups 1 and 2) or first SL BPN dose (Group 3), or any ongoing event on the date of first dose that worsens in severity after date of randomization. Only TEAEs with an onset date prior to date of last dose + 30 days will be tabulated in summary tables. For the purpose calculating treatment emergence and inclusion in summary tables, incomplete onset dates will be imputed as detailed in Appendix A.

TEAEs will be summarized by the number and percent of subjects in each primary SOC and preferred term. Subjects will be counted only once for each primary SOC and each preferred term. Summary tables of TEAEs by primary SOC, preferred term and intensity will be provided. If a subject has more than one TEAE coded to the same preferred term, the subject will be counted only once for that preferred term by using the event with the highest intensity. Similarly, if a subject has more than one TEAE within a primary SOC category, the subject will be counted only once in that SOC category by using the event with the highest intensity. TEAEs by primary SOC, preferred term and relationship to study drug will be provided as well. If a subject has more than one TEAE coded to the same preferred term, the subject will be counted only once for that preferred term by using the most related event. Similarly, if a subject has more than one TEAE within a primary SOC category by using the most related event. In addition, serious adverse events (SAE) by primary SOC and preferred term will be provided. Deaths and SAEs will be summarized similarly to AEs. All adverse event tables will also include the total number of events, counting multiple events per subject.

Injection related TEAEs, Other (non-injection related) TEAEs as well as all TEAEs will be presented by treatment group and overall. Summaries of these TEAE subsets will be presented for the following categories:

- Study drug related
- Intensity
- Relationship to injection
- Serious
- AEs which led to discontinuation
- SAEs which led to discontinuation
- TEAEs occurring in 5% or greater of any treatment group (by preferred term)

In the AE summary, preferred terms within each SOC will appear in alphabetical order.

Frequencies for deaths and hospitalizations will also be summarized by treatment group and overall.

Other safety analyses will be performed as appropriate.

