## 10.5.1.2 Adverse Event Definitions

An AE is any unfavorable or unintended change in body structure (signs), body function (symptoms), laboratory result (e.g., biochemistry, ECG, etc.), or worsening of a pre-existing condition associated temporally with the use of the study drug whether or not considered related to the study drug.

A treatment-emergent AE is any condition that was not present prior to treatment with study drug but appeared following treatment, was present at treatment initiation but worsened during treatment, or was present at treatment initiation but resolved and then reappeared while the individual was on treatment (regardless of the intensity of the AE when the treatment was initiated).

All AEs, including either observed or volunteered problems, complaints, signs, or symptoms must be recorded on the AE page of the CRF, regardless of whether associated with the use of study drug. This would include AEs resulting from concurrent illness, reactions to concurrent medication use, or progression of disease states (excluding the disease under study). AEs should be recorded in standard medical terminology.

The Investigator will evaluate each AE for duration, intensity, and relationship to study drug, record the action taken, and any treatment given. Recurrent symptoms of a chronic pre-existing condition are not considered AEs unless they occur in a worse or unexpected pattern during study drug administration.

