### 10.5.1.3 Intensity of AEs

The intensity (or severity) of AEs is characterized as mild, moderate, or severe:

**Mild** AEs are usually transient, requiring no special treatment, and do not interfere with the subject's daily activities.

**Moderate** AEs introduce a low level of inconvenience or concern to the subject and may interfere with daily activities, but are usually ameliorated by simple therapeutic measures.

Severe AEs interrupt a subject's usual daily activity and typically require systemic drug therapy or other treatment.

When the intensity category of the AE changes more frequently than once daily, the maximum intensity for the event is recorded. If the intensity category changes after a number of days, then these sub-events or changes are recorded separately (i.e., having distinct onset and stop dates).

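### SAP 11.4 classifies and totals adverse events by record onset, but the protocol gives each multi-day intensity phase its own onset, so an improving pre-dose event can become treatment-emergent and one event can count several times

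*SAP*

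**What the plan says.** Protocol 10.5.1.3 has two recording rules. For rapid changes, "When the intensity category of the AE changes more frequently than once daily, the maximum intensity for the event is recorded". If the category changes after a number of days, "these sub-events or changes are recorded separately (i.e., having distinct onset and stop dates").

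Protocol 10.5.1.2 treats an event as treatment-emergent if it is new after treatment, or if it "was present at treatment initiation but worsened during treatment, or was present at treatment initiation but resolved and then reappeared" while on treatment. Improvement does not qualify.

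SAP 11.4 has a two-limb definition. Under the first limb a TEAE "is defined as any AE with an onset date on or after date of randomization" in Groups 1 and 2, or on or after the first SL BPN dose in Group 3. The second limb adds "any ongoing event on the date of first dose that worsens in severity after date of randomization". Only the second limb tests for worsening.

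On counting, SAP 11.4 states: "All adverse event tables will also include the total number of events, counting multiple events per subject". Subjects, by contrast, count once per system organ class and once per preferred term, at the highest intensity or closest relationship. The section also plans a table of preferred terms that reach 5% of any treatment group.

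Protocol 10.5.1.1 collects AEs from the signing of consent, and Tables 1 to 3 mark AE assessment at Screening. The same section also sends conditions already present before dosing to medical history.

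**The concern.** The protocol's recording rule and the SAP's classification rule do not fit together. When a pre-dose event eases from moderate to mild some days after dosing, the protocol creates a second record with a post-dose onset. That record meets the first limb of the SAP definition by date alone, so the worsening test in the second limb is never reached. An improvement would then be tabulated as emergent on treatment, although the protocol's own definition excludes it.

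The second effect concerns totals. An event that starts after dosing and passes through several intensity categories, each lasting days, becomes several records, and each adds to the event total. The total then depends on how often a change of category was seen and recorded, and the visit schedules differ between groups.

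Safety and tolerability is a secondary objective. Local reactions matter here because Protocol 10.5.7 has injection sites examined at every scheduled visit and Appendix 17.3 grades erythema and swelling on a 4-point scale. Only the second effect applies to them, since no injection-site reaction can precede the first CAM2038 injection.

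**Working it through.** The plan states no AE rate or expected count, so there is no figure to reproduce. The check applies the written rules to hypothetical courses.

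**Rules applied**

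- As written (Protocol 10.5.1.3 with the first limb of SAP 11.4): TEAE records = number of intensity phases with onset on or after Day 1. The pre-dose record carries one intensity and stops when the next phase starts, so it is not itself counted.
- Linked, under Protocol 10.5.1.2: 1 if the first phase starts on or after Day 1. If the event began earlier, 1 when a post-dose phase exceeds the pre-dose intensity, otherwise 0. None of the courses below resolves and returns.

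**Results**

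| Hypothetical course | As written | Linked |
|---|---|---|
| Pre-dose moderate, mild from Day 4 | 1 | 0 |
| Pre-dose severe, moderate from Day 4, mild from Day 8 | 2 | 0 |
| Pre-dose mild, moderate from Day 4 | 1 | 1 |
| Pre-dose mild, moderate from Day 4, mild from Day 8 | 2 | 1 |
| Post-dose mild Day 3, moderate Day 6, mild Day 9 | 3 | 1 |
| Post-dose, constant intensity | 1 | 1 |

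The first two rows show improvement counted as emergence. The fourth and fifth show one episode counted more than once.

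**Event totals.** If post-dose event j has k_j multi-day phases, the total as written is the sum of the k_j, and the number of episodes is the number of events. The relative inflation is (mean of k_j) − 1. The documents give no value for that mean.

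**Subject counts.** Splitting a post-dose event leaves the subject count unchanged, because each subject counts once per term. An easing pre-dose event adds one subject only if that subject has no other TEAE of the same term. With the group sizes in SAP 9.5 (about 16 in each of Groups 2 and 3; 20 to 24 in Group 1), one subject is worth:

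- 1/16 = 6.25%; 5% of 16 is 0.8, so one subject reaches the threshold.
- 1/20 = 5.0%; 5% of 20 is 1.0, so one subject reaches it.
- 1/24 = 4.17%; 5% of 24 is 1.2, so two subjects are needed.

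**The case against.** The strongest reply is that the SAP means the onset of the whole event. The protocol calls the pieces sub-events, which implies a parent. The second limb of the definition would also have little to do if every split record qualified by its own date. That reading would agree with Protocol 10.5.1.2. But the SAP does not state it, and it gives no rule by which a programmer could link the records.

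The second reply is that few pre-dose events reach the AE page. Protocol 10.5.1.1 sends pre-dosing conditions to medical history. Protocol 10.5.1.2 excludes recurrent symptoms of a chronic pre-existing condition unless they are worse or unexpected, and excludes progression of the disease under study. This stands and narrows the first effect: unworsened chronic-pain symptoms are largely kept out. It does not close the gap, because AEs are also collected from consent through a screening period of up to 21 days. It has no bearing on the repeat counting of post-dose events.

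The third reply, that subject-level tables are protected, is correct for post-dose events. A reader might infer that splitting raises AE incidence generally; the once-per-term rule does not support that. A reader might also infer that every intensity change makes a new record; the collapse of changes more frequent than once daily contradicts that.

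**Conclusion.** The mismatch is real. Followed literally, the stated rules give a result that the protocol's own definition excludes, and they let one episode count as several in the event totals. It affects descriptive safety tables, not the PK analyses.

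The size is bounded only per event. A post-dose event with k multi-day phases counts k times instead of once. One falsely emergent subject is 6.25%, 5.0% or 4.2% of a group of 16, 20 or 24. That alone puts a term in the 5% table in Groups 2 and 3, or in Group 1 at 20 subjects, but not in Group 1 at 24. It assumes that the pre-dose event was entered on the AE page, was still present at dosing, eased afterwards, and was that subject's only TEAE record for the term.

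A reader might go further and attach an overall percentage to the inflation, or assume that each easing pre-dose event adds a false subject. The documents support neither: they give no AE counts or rates of intensity change, and a subject who already has a TEAE of that term is not counted again.

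**What to change.** Amend SAP 11.4 as follows.

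- Link contiguous records of the same preferred term in the same subject. For injection-site reactions, also require the same injection site. If the CRF has a parent-AE identifier, use that instead.
- Count each linked episode once, with the onset of its first record and its maximum post-dose intensity.
- Treat an episode that began before first dose (Group 3: first SL BPN dose) as a TEAE only if its post-dose intensity exceeds the last pre-dose intensity, or if it resolved and then came back, as in Protocol 10.5.1.2.
- State that event totals count episodes, not records.

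The injection-site condition is needed because Group 1 is injected weekly at rotating sites. Without it, a reaction that ends at one site on the next injection day could be merged with a new reaction at another site. Protocol Appendix 17.2 has the injection location recorded in the EDC; the documents do not show whether an AE record carries it, so this needs checking.

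The cost is SAP wording and a short programming rule, with no change to trial conduct. SAP 9.3 allows Groups 1 and 2 to be locked and analyzed before Group 3, so the change should be made before that first lock. The downside is that adjacent but distinct episodes of one term may occasionally be merged.
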